
 
Invasive Mechanical Ventilation / extracorporeal membrane oxygenation (ECMO):
 
Ventilator / ECMO use up to Day 29.
 
Incidence and duration of new mechanical ventilation or ECMO use during the study.
 
	
 
Days of invasive mechanical ventilation/ECMO (if applicable) up to Day 29.
 

 
Hospitalization
 
Duration of hospitalization (days).
 
	
 
Days of hospitalization as of Day 29 and day 120
 

Mortality 
 
15-day mortality
 
29-day mortality
 
120-day mortality
 
	
 
Date and cause of death (if applicable)
 

To evaluate the safety of CCP as compared to the control arm as assessed by:	• SAEs

 
Cumulative incidence of SAEs through Day 29.
 
Cumulative incidence of Grade 3 and 4 clinical and/or laboratory AEs through Day 29.
 
Transfusion associated adverse events
 
	
 
Grade 3 and 4 AEs
 
Grade 2 or higher AE's attributed to CCP
 

 
Exploratory Objectives
 
To evaluate the virologic efficacy of CCP
 
	

 
as compared to the control arm as assessed by:
 
Percent of subjects with SARS-CoV-2 detectable in nasal sample at Days 1,5,8,15
 
Quantitative SARS-CoV-2 virus in NP/MTN sample at Days 1,2,5,8,15
 
	
 
Qualitative and quantitative polymerase chain reaction (PCR) for SARS-CoV-2 in NP/MTN swab on Day 1,2,5,8,15 (while hospitalized)
 

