
 
Oxygenation:
 
Oxygenation use up to Day 90.
 
Incidence and duration of new oxygen use during the study.
 
Oxygen requirement on day 1,2,5,8,15, 29
 
	
 
Days of supplemental oxygen (if applicable) up to Day 29
 
PaO2/FiO2 ratio or SpO2/FiO2
 
O2 requirement at day 120
 

 
Non-invasive ventilation/high flow oxygen:
 
Non-invasive ventilation/high flow oxygen use up to Day 29.
 
Incidence and duration of new non-invasive ventilation or high flow oxygen use during the study.
 
	
 
Days of non-invasive ventilation/high flow oxygen (if applicable) up to Day 29
 

 
Invasive Mechanical Ventilation / extracorporeal membrane oxygenation (ECMO):         
 
Ventilator / ECMO use up to Day 29.
 
Incidence and duration of new mechanical ventilation or ECMO use during the study.
 
 
 
	
 
Days of invasive mechanical ventilation/ECMO (if applicable) up to Day 29.
 

 
Hospitalization
 
Duration of hospitalization (days).
 
	
 
Days of hospitalization as of Day 29 and day 120
 

Mortality 
 
15-day mortality
 
29-day mortality
 
120-day mortality
 
	
 
Date and cause of death (if applicable)
 

To evaluate the safety of CCP as compared to the control arm as assessed by:	• SAEs

 
Cumulative incidence of SAEs through Day 29.
 
Cumulative incidence of Grade 3 and 4 clinical and/or laboratory AEs through Day 29.
 
Transfusion associated adverse events
 
	
 
Grade 3 and 4 AEs
 
Grade 2 or higher AE's attributed to CCP
 

 
Exploratory Objectives         
 
To evaluate the virologic efficacy of CCP as compared to the control arm as assessed by:
 
 
 
Percent of subjects with SARS-CoV-2 detectable in NP/MTN sample at Days 1,5,8,15
 
Quantitative SARS-CoV-2 virus in NP/MTN sample at Days 1,2, 5,8,15
 
	
 
Qualitative and quantitative polymerase chain reaction (PCR) for SARS-CoV-2 in NP/MTN swab on Day 1,2,5,8,15 (while hospitalized)
 

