# 7.2 Definitions

1. **Adverse Event (AE):** Any untoward medical occurrence in a clinical investigation subject who has received a study intervention and that does not necessarily have to have a causal relationship with the study product. An AE can, therefore, be any unfavorable and unintended sign (including an abnormal laboratory finding, for example), symptom, or disease temporally associated with the use of the study product, whether or not considered related to the study product.

2. Serious Adverse Event (SAE): Any adverse event that results in any of the following outcomes:

- 1. Death
- 2. Life-threatening (immediate risk of death)
- 3. Prolongation of existing hospitalization
- 4. Persistent or significant disability or incapacity

5. Important medical events that may not result in death, be life threatening, or require intervention or escalation of care may be considered a serious adverse event when, based upon appropriate medical judgment, they may jeopardize the subject and may require medical or surgical intervention to prevent one of the outcomes listed in this definition. Examples of such medical events include allergic bronchospasm requiring intensive treatment in an emergency room or at home, blood dyscrasias or convulsions that do not result in inpatient hospitalization.

- 3. **Unexpected Adverse Event (UAE):** An adverse reaction, the nature or severity of which is not consistent with the investigator's brochure.
- 4. Serious and Unexpected Suspected Adverse Reaction (SUSAR): An adverse reaction, the nature of which is not consistent with the investigator's brochure with severity as defined by SAE above.
- 5. Unanticipated Problem (UP): Unanticipated Problem that is not an Adverse Event (e.g. breaches of confidentiality, accidental destruction of study records, or unaccounted-for study drug).
- 6. **Protocol Deviation:** Deviation from the IRB-approved study procedures. Designated serious and nonserious
- 7. Serious Protocol Deviation: Protocol deviation that is also an SAE and/or compromises the safety, welfare or rights of subjects or others

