# 7.3 Safety Reporting Requirements

#### 7.3.1 **Reporting Interval**

All grade 3 and 4 AE's, grade 2 AE attributed to study product and SAEs will be documented from the first administration of study product. These AEs and SAEs will be followed until resolution even if AEs extend beyond the study-reporting period. Resolution of an adverse event is defined as the return to pre-treatment status or stabilization of the condition with the expectation that it will remain chronic. At any time after completion of the study, if the investigator becomes aware of a SAE that is suspected to be related to study product.

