# 7.3.3 Assessment of Seriousness

- 1. Event seriousness will be determined according to the protocol definition of an SAE
- 2. Assessment of Severity

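### The SAE list omits new inpatient admission although its own example presumes it, so a readmission after discharge is not serious by default

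*Combined protocol and SAP*

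**What the plan says.** Section 7.2 defines an SAE as "Any adverse event that results in any of the following outcomes" and then numbers five items: death; a life-threatening event; "Prolongation of existing hospitalization"; lasting or significant disability or incapacity; and important medical events. The fifth item is permissive. Such events "may be considered a serious adverse event when, based upon appropriate medical judgment, they may jeopardize the subject", and its examples include "blood dyscrasias or convulsions that do not result in inpatient hospitalization".

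Section 7.3.3 makes this list the governing rule: "Event seriousness will be determined according to the protocol definition of an SAE". Section 7.3.1 sets what is recorded: "All grade 3 and 4 AE's, grade 2 AE attributed to study product and SAEs will be documented".

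The safety objective in sections 3 and 5.1 has three parts: "Cumulative incidence of SAEs through Day 29", "Cumulative incidence of Grade 3 and 4 clinical and/or laboratory AEs through Day 29", and transfusion-associated adverse events. The SAE definition is also used for SUSARs and serious protocol deviations (7.2) and in the study halting criteria (8.1).

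**The concern.** All participants are in hospital at enrolment, and many can be expected to go home within the 29-day SAE window. The study procedures provide for this, with telephone contact as an alternative at Day 15 and Day 29. From discharge onwards there is no existing stay to prolong. The hospitalisation event that can then occur is a new admission, and the list leaves that out.

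Whether a readmission is an SAE then depends on who assesses it. Two investigators could class the same event differently without either departing from the protocol. In a trial of 50 patients, a few events classed one way or the other can change the safety summary, and the SUSAR and halting rules inherit the same uncertainty.

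**Working it through.** No arithmetic applies. The document gives no SAE or readmission rate and states no figure to reproduce. The check is a reading of the sections against each other.

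**1. Does any listed outcome cover a new admission as such?**
- Items 1, 2 and 4 (death, life-threatening, disability): only if the event also has that outcome.
- Item 3 (prolongation): no, because a discharged patient has no existing stay.
- Item 5 (important medical events): not automatically; only if judged so.

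New admission is therefore a criterion in 0 of 5 items and is mentioned in 1 of 5, in the examples to item 5. The items run from 1 to 5 without a gap, and no other section adds the missing outcome.

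**2. Is the list consistent with its own example?** Item 5 is for events that do not have one of the outcomes in items 1 to 4. Describing a convulsion as one that did not lead to admission marks it as residual only if admission is itself a listed outcome. As written, a convulsion without admission is a named example of a possibly serious event, while a convulsion that causes readmission meets none of items 1 to 4 because of that readmission.

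**3. Does item 5 close the gap?** Only partly. It is discretionary. It is also tied to intervention that prevents one of the outcomes in the same definition. Since admission is not one of those outcomes, an event that threatens nothing more than admission does not literally qualify. The omission thus narrows the fallback as well as the main list.

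**4. Would the event be recorded anyway?** Section 7.3.1 has three routes: Grade 3 or 4, Grade 2 attributed to study product, or SAE. A readmission for an unattributed event below Grade 3 that is not judged serious fits none of them. How often an event leading to admission would be graded below 3 depends on the DAIDS table, which the protocol cites but does not reproduce.

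**5. What depends on the definition?**
- The SAE incidence through Day 29 (sections 3 and 5.1).
- The SUSAR definition, which takes its severity from the SAE definition, and the serious protocol deviation definition (7.2).
- The halting criterion under which a single SAE associated with study product stops enrolment and dosing for ad hoc review (8.1, item 3).

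**The case against.** The best defence is that little would be lost in practice. A readmission that is fatal, life-threatening or disabling is already an SAE. Item 5 takes in others, and its example helps: an investigator who may call a convulsion serious when it does not lead to admission would hardly call it non-serious when it does. Section 7.3.2 leaves every determination of seriousness to a qualified investigator, so judgment is not peculiar to item 5. Section 8.1, item 6, lets the responsible physician's judgment trigger a halt. AE evaluation already takes place at the Day 15, 29 and 120 contacts, and days of hospitalisation are an outcome at Day 29 and Day 120.

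Most of this stands, and it limits the point. It does not remove it: items 1 to 4 tie the judgment to a stated outcome, whereas item 5 permits without requiring. Collecting days in hospital does not class the event that caused them.

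A reader might infer four stronger things that the document does not support:
- *That readmissions are left out of the safety endpoint.* They can enter through items 1, 2, 4 or 5, as Grade 3 or 4 AEs, or as transfusion-associated AEs.
- *That readmissions up to Day 120 are lost from it.* The SAE incidence stops at Day 29, so later readmissions would lie outside it under any wording.
- *That the omission favours one arm.* This needs plasma to speed discharge and investigators to leave readmissions unclassified. The document establishes neither.
- *That the number of missed events can be calculated.* The ordinal table in 6.1 puts 16% + 16% = 32% of control (8 of 25) and 28% + 32% = 60% of active patients (15 of 25) out of hospital. But the table states no day, its active column is a power scenario rather than a forecast, and a status snapshot is not the number ever at risk. Any readmission rate applied to it would be an assumption.

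**Conclusion.** The SAE definition in 7.2 is internally inconsistent, and nothing elsewhere repairs it. A readmission after discharge is not an SAE by default. Unless it is fatal, life-threatening or disabling, its status rests on discretion under item 5, and some readmissions need not be documented as AEs at all. The SAE incidence through Day 29 may be under-counted, and it and the SUSAR and halting rules may be applied inconsistently.

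The size cannot be estimated from the document. The conclusion rests on the text alone and on one factual premise, that some participants leave hospital before Day 29. The case for correction is that the error is plain and the remedy cheap, not that a large number of events has been shown to be at risk.

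**What to change.** Reword item 3 of the SAE definition in 7.2 as: *Inpatient hospitalization (including readmission after discharge) or prolongation of existing hospitalization*. This makes the item 5 example consistent with the list. Classify readmissions found at the existing AE evaluations on that basis; no new visit is needed, and the Day 15 and Day 29 contacts already cover the endpoint window.

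The cost is one line of text and a few more SAE reports. The sponsor should note one consequence: a readmission judged associated with study product would then fall under the single-SAE halting criterion in 8.1 without an item 5 judgment. Section 7.3.4 reserves that association for events with no other explanation, so readmissions explained by another cause would not trigger it.

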# 7.3 Safety Reporting Requirements

#### 7.3.1 **Reporting Interval**

All grade 3 and 4 AE's, grade 2 AE attributed to study product and SAEs will be documented from the first administration of study product. These AEs and SAEs will be followed until resolution even if AEs extend beyond the study-reporting period. Resolution of an adverse event is defined as the return to pre-treatment status or stabilization of the condition with the expectation that it will remain chronic. At any time after completion of the study, if the investigator becomes aware of a SAE that is suspected to be related to study product.

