# STUDY PROCEDURES

# 1. Study Protocol by Day:

### Day -2 to 1:

- A. Screening (must be completed before randomization)
- B. Informed consent (obtained before performing study related activities)
- C. Baseline Evaluation (at screening) (much of the information will be obtained from the medical record)
  - 1. Demographics: Age, sex, race
  - 2. Medical history:
    - Timing of exposure to COVID-19 source patient
    - Acute and chronic medical conditions that a risk factors for COVID
    - Medications, allergies
    - Any medical condition arising after consent to be recorded as AE.
  - 3. COVID-19 symptom screen: Fevers, cough, shortness of breath.
  - 4. History of illness: Onset of symptoms
  - 5. Vital signs
  - 6. Oxygenation status: current FiO2 or liters of O2, route of oxygen support, and oxygen saturation or Pa02 (if available)
  - 7. COVID-19 testing (RT-PCR) Per standard of care. Positive test PCR required within 14 days of screening
  - 8. Baseline Basic Lab Testing
    - ABO Blood typing, CBC with absolute lymphocyte count, comprehensive metabolic panel, inflammatory and coagulation markers (d-dimer, hsCRP, PT/INR, PTT)
  - 9. For females of childbearing potential, urine or serum pregnancy test
    - Results from laboratory tests obtained up to 14 days before enrollment may be used for the pregnancy test
- D. Determination of eligibility
  - Inclusion/exclusion criteria age
  - Consent
  - Positive for COVID-19 within past 14 days
  - not already an ICU patient
  - Within 14 days of first sign of illness or within 72 hours of admission

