#### Day 1:

- 1. Randomization of eligible subject
- 2. Study Plasma Administration:
  - 1 unit of plasma will be transfused within 24 hours of enrollment
  - Time at start and end of infusion will be recorded
  - Vital signs will be measured immediately prior to infusion, 10-20 minutes after start of infusion, at completion of infusion and 30-60 minutes after the end of the infusion
- 4. Assessment of clinical status (8-point ordinal scale)
- 5. New medical conditions, concomitant medication, AE evaluation

7. Oxygenation status: current FiO2 or liters of O2, route of oxygen, and oxygen saturation or PaO2 (if available)

8. COVID-19 testing (RT-PCR): nasopharyngeal samples

10. Stored samples for future studies (3 EDT tubes and 1 SST). This will include serological testing for SARS CoV-2 antibodies

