#### 7.1.1 Potential risks

- 1. Risks of Plasma: Fever, chills, rash, headache, serious allergic reactions, TRALI, TACO, transmission of infectious agents
- 2. Risks of Phlebotomy: local discomfort, bruising, hematoma, bleeding, fainting,
- 3. Total blood draws will not exceed 500 mL
- 4. Risks of oropharyngeal and throat swab: local discomfort, vomiting, coughing

Alternatives: The alternative to participation in this study is routine care.

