# 8.2 Halting Criteria/Rules for Subject Infusion:

Infusion of study drug will be halted if any of the following manifestations of anaphylaxis develop and will not be restarted:

- Skin or mucous membrane manifestations: hives, pruritus, flushing, swollen lips, tongue or uvula
- Respiratory compromise: dyspnea, wheezing, stridor, hypoxemia
- A decrease in systolic blood pressure to < 90 mmHg or >30% decrease from baseline or a diastolic drop of >30% from baseline.
- Tachycardia with an increase in resting heart rate to > 130 beats per minute; or bradycardia <40 that is associated with dizziness, nausea or feeling faint.

• Any other symptom or sign which in the good clinical judgment of the study clinician or supervising physician warrants halting the infusion. For example, the rapid onset of gastrointestinal symptoms, such as nausea, vomiting, diarrhea, and cramps, for instance, may be manifestations of anaphylaxis and may warrant an immediate halt prior to meeting full SAE criteria

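### The AE rules conflict on scope and start, and 7.3.1 does not require Grade 1 (or unattributed Grade 2) infusion reactions to enter the study AE data

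*Combined protocol and SAP*

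**What the plan says.** The protocol states the AE rule in three places.

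- **Section 7.3.1, Reporting Interval.** Scope: "All grade 3 and 4 AE's, grade 2 AE attributed to study product and SAEs will be documented". Start: these "will be documented from the first administration of study product".
- **Section 7.2, Definitions.** An AE is "Any untoward medical occurrence in a clinical investigation subject who has received a study intervention". This agrees with 7.3.1 that nothing before infusion is an AE.
- **Section 5.4, Day -2 to 1, under medical history.** "Any medical condition arising after consent to be recorded as AE". No grade, attribution or infusion condition is attached.

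Section 8.2 ends the infusion, without restart, for any one of a list of signs. The list includes "Skin or mucous membrane manifestations: hives, pruritus, flushing, swollen lips, tongue or uvula", with no minimum grade, and 8.2 foresees some halts before SAE criteria are fully met. Section 5.3.6 says most plasma reactions are fairly minor and allows slowing, pausing or stopping. On infusion conduct, the Day 1 procedures state "Time at start and end of infusion will be recorded" and ask for vital signs around the infusion. They do not ask for the reason for an interruption.

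**The concern.** Two people applying the protocol faithfully could build different AE datasets, depending on which rule they took as governing. Section 6.2.4 compares AE rates between arms with Fisher's exact test, so the rule decides what is counted.

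The second issue is that three parts of the plan look to minor reactions. The objectives tables (sections 3 and 5.1) list transfusion-associated adverse events as a safety item with no grade limit beside it. Section 7.1.2 promises to say whether reactions are more frequent, less frequent or the same as with standard plasma. Criterion 5 in section 8.1 asks the safety monitoring committee (SMC) to weigh patterns of events that look minor one at a time. If 7.3.1 governs, the mildest reactions need not be in the AE data that would feed all three.

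**Working it through.** No design figure is involved, so the check sets the rules side by side and then does one piece of arithmetic on timing.

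**Scope.** Clinical events only; section 7.3.2 has a separate rule for laboratory changes of 2 standard deviations above baseline.

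| Event | Baseline line in 5.4 | 7.2 and 7.3.1 |
|---|---|---|
| Any condition between consent and infusion | AE | Not an AE |
| Grade 3-4, or serious, after infusion starts | AE | Documented |
| Grade 2, non-serious, associated | AE | Documented |
| Grade 2, non-serious, not associated | AE | Not required |
| Grade 1, non-serious | AE | Not required |

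The rules agree on two rows of five and differ on three.

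**Which infusion reactions fall in the last two rows.** Under section 7.3.4 an event is associated only if it is temporally related and no other cause explains it. Hives or itching at Grade 2 during an infusion would usually be judged associated, and so documented. Section 7.1.1 gives "Risks of Plasma: Fever, chills, rash, headache, serious allergic reactions, TRALI, TACO" among others. Of these, chills or headache at Grade 2 could be put down to COVID-19 and fall outside 7.3.1. Grade 1 reactions of any kind fall outside it. Section 7.3.1 makes no exception for a reaction that changes the infusion, so this holds even where 5.3.6 or 8.2 leads to slowing or stopping. The two sections also handle hives and itching differently: 5.3.6 generally allows continuation after a pause, and 8.2 does not allow a restart. Bedside practice may therefore vary, which makes a recorded reason more useful.

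**Length of the period in dispute.**

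- Short reading: section 5.2 counts a subject as enrolled from consent, and the Day 1 procedures require transfusion within 24 hours of enrollment. Consent to infusion is then at most about 24 hours.
- Long reading: Table 1 puts consent in the screening column, up to 3 days before enrollment, and section 5.3.6 allows 24 hours from randomization to infusion. With randomization on the enrollment day, 3 days + 1 day = about 4 days.

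**Frequency.** This cannot be derived. It depends on how the signs in 8.2 would be graded in the DAIDS table, which the documents cite but do not reproduce, and on reaction rates by grade, which they do not give.

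**The case against.** The best defense is that the threshold is deliberate and coherent. The safety endpoint column in sections 3 and 5.1 lists SAEs, Grade 3 and 4 AEs, and attributed AEs of Grade 2 or higher, which is what 7.3.1 collects. Selective collection by grade is a legitimate choice. That stands, and it is why the threshold should remain for general AEs.

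It can also be said that the two halves of the point cancel: if the baseline line governs there is no low-grade gap, and if 7.3.1 governs the start is settled. But the protocol does not say which governs. The more natural reading is 7.3.1, since section 7.3 sets reporting and 7.2 agrees with it. On that reading the low-grade gap is real and the baseline line needs correcting.

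Four stronger conclusions might tempt a reader, and the documents do not support them.

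- *Low-grade reactions would go unrecorded, or would be seen only if someone happened to write them under an open heading.* Section 9.6.1 requires the medical record, the primary source document, to hold any AE during the trial, with no grade limit. AE evaluation is scheduled on Day 1 and, for those still in hospital, on Day 2. Section 7.4.1 lets the SMC review study data, including unblinded data, and criterion 5 is not confined to the 7.3.1 list. The events should be in source; what is not required is their transfer to the study AE data.
- *The symptom screen shows the size of the gap because it omits most transfusion signs.* The screen, "COVID-19 symptom screen: Fevers, cough, shortness of breath", is a COVID-19 instrument not meant to detect transfusion reactions. What it leaves out says nothing about the AE evaluation.
- *Infusions will often be halted for events that are never documented as AEs.* Section 8.2 calls its signs manifestations of anaphylaxis. Many could be graded 2 or higher and attributed, or judged important medical events under 7.2. The Grade 1 share is unknown.
- *The CRF has no place for these reactions.* The CRF is not among the documents. One can say only that the protocol does not require the entry.

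**Conclusion.** The point holds as a minor one. The baseline line in 5.4 contradicts 7.2 and 7.3.1 on both scope and start, over a period of about 24 hours to about 4 days before infusion. Separately, 7.3.1 does not require Grade 1 infusion reactions, or Grade 2 reactions judged not associated, to enter the study AE data, even when they alter or end the infusion. The input to the transfusion-associated item, the 7.1.2 comparison and criterion 5 is therefore incomplete, not absent.

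The second part assumes that 7.3.1 is the governing rule and that the AE data are built from it; no other provision requires the transfer. No size of effect is claimed. The primary endpoint, the sample size and the listed safety endpoints are unaffected.

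**What to change.** Amend 7.3.1 along these lines:

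> AE recording begins at the start of infusion. From then until the Day 2 assessment, or discharge if earlier, AEs of every grade and attribution are documented in both arms, together with the reason for any slowed, paused or halted infusion. After that point, documentation covers SAEs, AEs of Grade 3 or 4, and Grade 2 AEs attributed to study product.

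Replace the baseline line in 5.4 with a reference to 7.3.1, and state that conditions arising between consent and infusion are recorded as new medical conditions, not AEs. Give the SMC the infusion-reaction listing by arm for criterion 5, and use the same listing for the 7.1.2 comparison. Leave the safety endpoint column in sections 3 and 5.1 as it is.

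The cost is a short amendment, one cross-reference and a brief CRF entry for about 50 infusions, at AE evaluations already scheduled on Days 1 and 2. The downside is that some mild COVID-19 symptoms will be listed in both arms.
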